8.1.5. Early Termination Visit

In the case a patient prematurely discontinues study treatment, an unscheduled visit should occur with assessments normally planned at the (EOT) visit (it should take place within 5 days of treatment discontinuation, if possible). Patients who permanently discontinue study drug during the DBTP should then resume the original study schedule (except for study treatment administration) until end of the DBTP, and all efforts should be made to perform the week 24 assessments at week 24 (regardless of study treatment administration). All patients who prematurely discontinue study treatment (either in the double-blind period or the open-label period) should be followed for at least 24 weeks from the last dose of study drug, and a final end of study visit can take place with assessments as specified in the end of study visit (ie, follow up visit).

Sexually active WOCBP who discontinue the study prematurely should be reminded at the unscheduled visit following treatment discontinuation to maintain highly effective contraceptive measures for 24 weeks after the last dose of study drug. At this visit, the patient will be provided 5 urine pregnancy tests with instructions to test for pregnancy 4 weeks after this visit and Q4W thereafter. The patient will also be notified of Q4W follow-up phone calls to confirm continued contraception use and pregnancy reporting and to obtain the results of the urine pregnancy test.

If a WOCBP is lost to follow-up, sites should attempt a minimum of 2 telephone calls. If the patient cannot be reached on the second attempt, a formal letter will be issued from the site to the patient that reminds the patient of the importance of continued use of highly effective contraception use for at least 6 months after the last dose of study drug.

8.1.6. Unscheduled Visits

All attempts should be made to keep patients on the study schedule. Unscheduled visits may be necessary to repeat testing following abnormal laboratory results, for follow-up of AEs, or for any other reason, as warranted.

8.2. Study Procedures

8.2.1. Procedures Performed Only at the Screening/Baseline Visit

The following procedures will be performed for the sole purpose of determining study eligibility or characterizing the baseline population:

- Hepatitis B Surface Antigen
- Hepatitis C Antibody
- TSH
- FSH

8.2.2. Efficacy Procedures

All laboratory samples will be collected before the dose of study drug is administered.

Blood samples for lipid panels should be collected in the morning, in fasting condition (ie, overnight, at least 8 hours fast, only water) for all clinic visits. Alcohol consumption within

48 hours, and smoking or intense physical exercise within 24 hours, preceding blood sampling are discouraged.

Total-C, HDL-C, TG, Apo B, Apo A-1, Lp(a), and Apo CIII will be directly measured by the central laboratory. LDL-C will be calculated using the Friedewald formula. If TG values exceed 400 mg/dL (4.52 mmol/L) or if calculated LDL-C values are below 25 mg/dL (0.65 mmol/L), LDL-C will be measured via the beta quantification method (rather than via the Friedewald formula). Non-HDL-C will be calculated by subtracting HDL-C from the total-C. Ratio Apo B/Apo A-1 will be calculated. All lipid results will be blinded from after the randomization visit until the week 36 visit. Every effort should be made to continue to keep the sponsor blinded to all lipid parameters for the duration of the study. No attempts should be made by the investigator or patient to have the patient's lipid values independently evaluated after randomization until after the end of study visit.

Detailed procedures of sample preparation, storage, and shipment are provided in the laboratory manual.

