10.4.3.2. Secondary Efficacy Analysis

For the key secondary efficacy endpoints (defined in Section 4.2.2) and other secondary efficacy endpoints (described in Section 4.2.3) collected in the DBTP, descriptive summaries and analyses will be performed in the ITT population, using values obtained regardless of adherence to study treatment and subsequent therapies (ITT estimand).

For descriptive summaries, percent change, and when appropriate change from baseline, in calculated LDL-C, total-C, TG, non-HDL-C, Apo B, Lp(a), and Apo CIII will be provided at each time point. All measurements, scheduled or unscheduled, will be assigned to analysis windows defined in the SAP in order to provide an assessment for these time points. Laboratory assessments other than the ones provided by the central laboratory will be excluded. For TG, measurements on non-fasting patients will be excluded. The time profile of each parameter will be plotted by treatment group with the corresponding SEs.

Multiple types of measurements are planned to be analyzed during differing time points in the trial, specifically continuous measurements expected to have a normal distribution (example: percent change in calculated LDL-C), continuous measurements expected to have a non-normal distribution (example: TG), and binary measurements (example: proportion of patients reaching LDL-C <100mg/dL).

I. Continuous endpoints anticipated to have a normal distribution

Continuous secondary variables defined in Section 4.2.2 and Section 4.2.3 anticipated to have a normal distribution (ie, lipids other than TG and Lp[a]) will be analyzed using the same MMRM

model as for the primary endpoint. Specifically, the model will contain fixed categorical effects of treatment group, randomization strata, planned time points up to the time point of interest, strata-by-time point interaction and treatment-by-time point interaction, as well as the continuous fixed covariates of corresponding baseline value and baseline value-by-time point interaction.

II. Continuous endpoints anticipated to have a non-normal distribution

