4.7. Efficacy Variable

Efficacy will be assessed through the following lipid parameters: calculated LDL-C (using the Friedewald formula), total-C, TG, non-HDL-C (calculated by subtracting HDL-C from Total-C), Apo B, Apo CIII, and Lp(a). All lipid parameters will be collected over the course of the study and sent to a central laboratory for evaluation, including scheduled and unscheduled blood draws.

All lipid values obtained during the study (scheduled or unscheduled), regardless of fasting status (fasting or not fasting), can be used to provide a value for the primary and secondary efficacy endpoints, with the following exceptions:

1. Only fasting TG measurements will be included in the analysis. TG measurements with missing fasting status will be excluded from the analyses.
2. On the day of apheresis, any lipid values collected after apheresis for the respective visit will be excluded from the efficacy analyses.

All measurements will be assigned to efficacy analysis windows defined in Appendix 10.2 of this SAP, with the intent to provide an assessment for week 4 to week 24 time points. For all time points post-baseline, the value used for the analyses at a given time point (e.g. at week 24) is the value obtained within the corresponding efficacy analysis window. The baseline value is defined as the last available measurement prior to the date of the first double-blind study treatment administration (applicable to measurement derivations during both DBTP and OLTP). For patients randomized and not treated, the baseline value is defined as the last available value prior to the date of randomization.

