4.7.1. Primary Efficacy Variable (s)

The primary endpoint is the percent change in calculated LDL-C from baseline to week 24. The primary endpoint is defined as: $100 \times (\text{calculated LDL-C value at week 24} - \text{calculated LDL-C value at baseline}) / \text{calculated LDL-C value at baseline}$.

The baseline LDL-C value will be the last calculated LDL-C value obtained before the first dose of double-blind-study drug. The calculated LDL-C at week 24 will be the LDL-C value obtained within the week 24 efficacy analysis window, regardless of adherence to treatment and subsequent therapies (intent-to-treat [ITT] estimand).

All calculated LDL-C values (scheduled or unscheduled, fasting or not fasting) may be used to provide a value for the primary efficacy endpoint, if appropriate, according to the above definition.

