6.4. Visit Windows

Visit windows will be programmatically imposed on those efficacy and safety measures repeatedly collected over the course of the study. These visit windows are derived from the number of days in study, specifically assigning day ranges to represent the study assessment schedule provided in the protocol. Data analyzed by time point (including efficacy, laboratory safety data, vital signs, ECG, quality of life, drug concentration and ADA) will be summarized using the analysis windows given in Appendix 10.2 (i.e. efficacy analysis windows for efficacy and global analysis windows for safety). These analysis windows will be applicable for all analyses, and they are defined to provide more homogeneous data for time point-specific analyses. If multiple valid values of a variable exist within an analysis window, the nearest from the targeted study day will be selected for analysis, unless otherwise specified. If the difference is a tie, the value after the targeted study day will be used. If multiple valid values of a variable

exist within a same day, then the first value of the day will be selected when time is available, else the scheduled visit will be selected.

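### Fasting status decides whether a TG value is usable but not whether the LDL-C calculated from it is, and the choice of value within a window ignores it too

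*Protocol*

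**What the plan says.** The protocol wording below is the same in the adult version and in the version that admits patients from 12 years.

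- **How LDL-C is obtained.** Protocol 8.2.2: "LDL-C will be calculated using the Friedewald formula". Beta quantification replaces it only when TG is above 400 mg/dL or calculated LDL-C is below 25 mg/dL.
- **Intended sampling.** Protocol 8.2.2: "Blood samples for lipid panels should be collected in the morning, in fasting condition". This applies to all clinic visits.
- **TG as an endpoint.** SAP 4.7: "Only fasting TG measurements will be included in the analysis. TG measurements with missing fasting status will be excluded from the analyses". Protocol 10.4.3.2 agrees: "For TG, measurements on non-fasting patients will be excluded".
- **LDL-C as the primary endpoint.** SAP 4.7.1: "All calculated LDL-C values (scheduled or unscheduled, fasting or not fasting) may be used to provide a value for the primary efficacy endpoint".
- **Choice within a window.** SAP 6.4: "If multiple valid values of a variable exist within an analysis window, the nearest from the targeted study day will be selected for analysis". A tie goes to the later value. Among values from one day, the first is taken when the time is known. Fasting status is not a criterion.
- **Sensitivity analyses.** SAP 5.7.1.1 covers stratification errors, on-treatment values, non-GCP sites and missing data. None concerns fasting status.

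**The concern.** The plan treats one sample in two ways. If it was not fasting, its TG is judged unfit for analysis, but the LDL-C computed from that TG stays eligible for the primary endpoint. The TG exclusion shows that the sponsor expects some such samples. The switch to beta quantification above 400 mg/dL shows that the dependence of the formula on TG is recognised, but an ordinary post-meal rise stays below that trigger.

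A post-meal TG rise makes calculated LDL-C too low. At week 24 this overstates the reduction and can carry a patient over a responder cut-off. The proportions with at least 30% reduction, at least 50% reduction and LDL-C under 100 mg/dL are key secondary endpoints in a fixed testing sequence (SAP 4.7.2 and 5.7.2.5), where one failure ends confirmatory testing. With 19 planned placebo patients, one patient is 1/19 = 5.3 percentage points of that arm's response rate.

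**Working it through.** **Inputs from the documents.** 38 evinacumab and 19 placebo patients, difference 38 points, SD 35, two-sided 0.05, 90% power, 5% non-evaluable and 15% dropout (SAP 2.2). Week-24 visit on day 169 ± 1 (Protocol Table 3). Week-24 efficacy window from day 155 to 182, or to the first open-label dose day for patients who enter that period (SAP 10.2, Table 2).

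**Inputs assumed.** The documents give no non-fasting rate, no post-meal TG rise and no expected baseline LDL-C. They name the Friedewald formula without printing it; the standard form in mg/dL is LDL-C = TC − HDL-C − TG/5.

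**1. The plan's own figure.** A two-sample t-test with 28 and 14 evaluable patients has 89.9% power; with 30 and 15 it has 91.9%. So 45 evaluable patients are needed, and 45/0.80 = 56.25, which rounds up to 57 at 2:1. The stated size reproduces, and nothing here changes it.

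**2. Error in one sample.** Error in LDL-C = −(TG rise)/5.
- Rises of 50, 100 and 150 mg/dL give −10, −20 and −30 mg/dL.
- At baseline 250 mg/dL that is 4, 8 and 12 percentage points; at 150 mg/dL it is 6.7, 13.3 and 20.

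**3. When a non-fasting value is chosen over a fasting one at week 24.**
- Fasting sample and first open-label dose on day 168: the window closes that day, so a draw on day 169 does not count.
- Fasting sample on day 170, non-fasting on day 168: a tie, and the later, fasting value is used.
- Non-fasting draw on day 169, fasting repeat on day 170 before the first open-label dose: the non-fasting value is nearer and is used.
- Fasting visit outside ±1 day, say day 172, and a non-fasting unscheduled draw on day 167: distances 3 and 2, so the non-fasting value is used. Footnote 2 to Protocol Table 3 allows for visits outside the window because of apheresis timing.
- Patient not entering the open-label period: the window runs to day 182, and any nearer non-fasting draw is used.

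**4. Shift in the mean difference.** Let f be the fraction of week-24 values that are non-fasting, r the TG rise on evinacumab relative to placebo, and B the baseline LDL-C. Then shift = f × (TG rise/5) × (1 − r)/B × 100.
- Low end: 0.05 × 10 × (1 − 0.5)/250 × 100 = 0.1 points.
- High end: 0.10 × 30 × (1 − 0.25)/250 × 100 = 0.9 points.
- Wider range (B 100 to 500 mg/dL, rise 25 to 100 mg/dL, r 0.25 to 1.0, f 0.05 to 0.20): from 0 when r = 1 to 0.20 × 20 × 0.75/100 × 100 = 3.0 points, with every input at its worst.

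For r below 1 the shift is towards no difference, because placebo looks better than it is.

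**5. Power with 30 and 15 evaluable.** 91.9% with no shift, 91.5% at 0.3 points, 90.4% at 1 point and 87.1% at the 3.0 extreme.

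**6. One patient near a cut-off.** Baseline 250 and true week-24 LDL-C 182.5 mg/dL is a 27% reduction. A 50 mg/dL TG rise turns 182.5 into 172.5, a 31% reduction, and the patient counts as a 30% responder.

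**The case against.** The other side has a good deal in its favour.

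- **Non-fasting samples are deviations.** Fasting is asked for at every clinic visit, and sites do not see post-randomization lipid results before week 36 (Protocol 8.2.2), so a lipid result cannot prompt a repeat draw before week 24. A reader might infer that non-fasting values routinely override fasting ones; step 3 shows that at week 24 this takes an unusual sequence of draws. That stands.
- **The difference between arms is not established.** A reader might take it as a fact that the error is smaller on evinacumab. Protocol section 1 makes this plausible: ANGPTL3 inhibits lipoprotein lipase, and a single 20 mg/kg dose lowered TG by a median 75% on day 4, against a 9% rise on placebo. Those were volunteers with modest lipid elevations, not HoFH patients four weeks after 15 mg/kg. That stands too.
- **Other endpoints do not use TG.** Apo B, non-HDL-C and TC are the first three key secondaries and give a useful cross-check. They cannot correct an LDL-C responder status.
- **Keeping all values is pre-specified and fits the ITT estimand.** This holds only in part. The estimand disregards adherence and later therapy, not the validity of a sample, and SAP 4.7 already excludes lipid values taken after apheresis on the same day.
- **A blanket preference for fasting values could do harm.** It could select day 155, two weeks after the week-20 dose on day 141, or a sample mismatched in apheresis or PCSK9-inhibitor timing, which Protocol 5.1 asks to be matched to baseline. This stands and limits the fix.

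**Conclusion.** The inconsistency is real and has a small effect. SAP 4.7 and 4.7.1 treat TG and the LDL-C derived from it differently, SAP 6.4 lets a non-fasting value be used in some cases where a fasting one exists, and no sensitivity analysis would show the effect.

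On the narrower assumptions in step 4, the mean difference shifts by less than 1 point of 38; with every input at its worst it shifts by 3.0. It moves towards zero if the TG rise is smaller on evinacumab, which is plausible but not shown for this population and dose. A non-fasting baseline value affects both arms alike in expectation. A reader might infer that the primary result is at risk; these figures do not support that. What remains is avoidable misclassification of individual patients near the 30%, 50% and 100 mg/dL cut-offs. This is a cheap improvement, not a flaw that calls the trial into question.

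**What to change.** Before the first-step database lock:

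1. **SAP 6.4.** When a fasting LDL-C and one that is non-fasting or of unknown status both lie within a few days of the target day and before the next dose, with comparable apheresis and PCSK9-inhibitor timing, use the fasting value. Otherwise keep the nearest value. The SAP should put a number on the few days.
2. **Primary analysis.** Keep a non-fasting value in the ITT analysis when it is the only one, so that no patient is lost.
3. **SAP 5.7.1.1 and 5.7.2.4.** Add one sensitivity run of the primary MMRM, and of the LDL-C responder endpoints, without non-fasting or unknown-status LDL-C. State how a non-fasting baseline is handled in that run.

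Beta quantification is not a ready substitute: Protocol 8.2.2 provides it only beyond the two triggers, so ordinary non-fasting samples will have no such value.

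The cost is a short addition to the SAP, one extra run and, in a few patients, a value slightly further from the target day.

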7.6.1. Blinding

Study patients, the principal investigators, and study site personnel will remain blinded to all randomization assignments throughout the DBTP (up to week 24). The Regeneron Study Director, Medical Monitor, Study Monitor, and any other Regeneron and contract research organization (CRO) personnel who are in regular contact with the study site will remain blinded to all patient randomization assignments.

Lipid results from blood samples collected after the randomization visit will not be communicated to the sites, and the sponsor's operational team will not have access to these laboratory results until after completion of the DBTP and the first-step analysis.

Although there is a slight color difference between the drug product and placebo product for IV infusion bag preparation, the color difference is not detectable when the investigational product is added to the IV infusion bag.

Further details are provided in the pharmacy manual.

After the end of the DBTP visit at week 24, the study becomes an open-label study.

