13. All end of treatment (EOT) assessments are to be performed and blood samples are to be collected before the dose of open-label study drug in all patients. For patients undergoing apheresis: Study assessments are to be performed and blood samples are to be collected immediately before the lipid-apheresis procedure; open-label study drug will be administered after the apheresis procedure.
14. In the OLTP, the HADS should be administered after the patients have been informed of their lipid results

8.1.4. Footnotes for Schedule of Events Table 4

1. ECG should be performed before blood samples are collected at visits requiring blood draws
2. WOCBP only, confirm required contraception use and reminder pregnancy reporting.
3. Including assay of total ANGPTL3
4. For patients who discontinue prematurely or who opt out of the OL study
5. Phone visits (PV) at weeks 56 and 64 to confirm required contraception use and obtain results of the home urine pregnancy test. Adverse events and concomitant medications will be collected

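### Protocol sections 7.6.1 and 8.2.2 give inconsistent rules for when post-randomization lipid results are released, and the week 36 rule can take effect before the first-step database lock

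*Protocol*

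**What the plan says.** Three places in the protocol govern who sees lipid results and when.

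- Section 7.6.1 (Blinding): "Lipid results from blood samples collected after the randomization visit will not be communicated to the sites". The same sentence adds that the sponsor's operational team "will not have access to these laboratory results until after completion of the DBTP and the first-step analysis". Grammatically that end date belongs to the operational team, and it may or may not be meant for sites too.
- Section 8.2.2 (Efficacy Procedures): "All lipid results will be blinded from after the randomization visit until the week 36 visit". The next sentence reads "Every effort should be made to continue to keep the sponsor blinded to all lipid parameters for the duration of the study". The paragraph then bars investigators and patients from having lipids "independently evaluated after randomization until after the end of study visit".
- Section 8.1.3, footnote 14 to Table 3, attached to the HADS at weeks 40 and 48: "In the OLTP, the HADS should be administered after the patients have been informed of their lipid results". The schedule in SAP Appendix 10.9 repeats this as footnote 15.

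Sections 7.6.1 and 8.2.2 have the same wording in both protocol versions (18 years and over, 12 years and over), so this is not a leftover from superseded text.

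On timing, all patients receive evinacumab from week 24 (day 169). The first-step analysis waits until every patient's week 24 data are collected and validated (protocol 10.4.9.1). Its cut-off is the last patient's week 24 visit (SAP section 7).

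**The concern.** A central laboratory cannot build a reporting rule from these sections, because they set different dates for the same results. The first-step analysis is one calendar event for the whole trial, whereas week 36 is counted separately for each patient. In staggered recruitment, early patients reach week 36 while the double-blind database is still open.

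The plan relies on masking until that lock. SAP revisions are to rest on blinded data review (SAP section 1), protocol deviations are reviewed on an ongoing basis (SAP 4.6), and investigators rate the severity and causality of double-blind adverse events. Protocol 7.6.2 also withholds treatment assignment from site staff during study conduct, except in an emergency. If a site received a patient's weeks 2-24 lipids at week 36, it could compare them with values after the open-label switch and form a view of the arm.

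There is also a practical conflict. If sites follow 7.6.1, early patients cannot be told their results before the week 40 HADS. If some sites follow 7.6.1 and others 8.2.2, the open-label HADS summary mixes informed and uninformed patients.

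**Working it through.** **1. The rules side by side**

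| Audience | 7.6.1 | 8.2.2 | HADS footnote |
|---|---|---|---|
| Sites | No release stated, or after the first-step analysis | Patient's own week 36 | Implied before week 40 |
| Patients | Not addressed separately | Patient's own week 36 | Before weeks 40 and 48 |
| Sponsor | Operational team: after the first-step analysis | Sponsor, unqualified: whole study, best efforts | Not addressed |

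For sites, either reading of 7.6.1 differs from week 36. For the sponsor, the unqualified sentence in 8.2.2 cannot hold literally, because the first-step analysis uses these lipid data.

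**2. How far apart the dates are**

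Table 3 gives week 24 as day 169, week 36 as day 253 and week 40 as day 281.

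- Week 36 minus week 24: 253 - 169 = 84 days = 12 weeks.
- Week 40 minus week 24: 281 - 169 = 112 days = 16 weeks.

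So anyone randomized more than 12 weeks before the last patient reaches week 36 before the last week 24 visit. Anyone more than 16 weeks ahead also reaches the week 40 HADS before it.

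**3. How many patients**

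The documents do not state accrual length or the lag from the last week 24 visit to lock. Assume uniform accrual over A weeks and a lag of L weeks. The share past week 36 at lock is (A - 12 + L)/A, bounded between 0 and 1.

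| Assumed A (weeks) | L = 0 | L = 8 |
|---|---|---|
| 12 | 0% | 67% |
| 16 | 25% | 75% |
| 26 | 54% | 85% |
| 52 | 77% | 92% |
| 78 | 85% | 95% |

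The two dates are compatible for every patient only if A + L is 12 weeks or less.

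**4. What a released profile would reveal, if weeks 2-24 were included**

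Inputs from protocol 10.2: difference 38 percentage points, SD 35, allocation 38:19. These reproduce the plan's sample size. A two-sample t-test gives 89.9% power at 28:14 and 91.9% at 30:15, and 45/0.80 = 56.25, which becomes 57 at 2:1. Nothing in this point changes that figure.

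Compare the mean of a patient's 7 double-blind values (weeks 2 to 24) with the mean of weeks 28 and 32. Assume that a placebo patient falls by 38 points on switching, that an evinacumab patient does not change, and that all pairs of values share one within-patient correlation r. Then:

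- SD of the contrast = 35 × √[(1 - r)(1/7 + 1/2)]
- Correct classification at the midpoint = Φ(38 / (2 × SD))

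| Assumed r | SD of contrast | Arm classified correctly |
|---|---|---|
| 0.4 | 21.7 | 81% |
| 0.6 | 17.7 | 86% |
| 0.8 | 12.5 | 93% |

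The benchmark is 38/57 = 67%, from guessing evinacumab every time. The correlations are not in the documents, and the whole calculation depends on weeks 2-24 being handed over.

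**5. If weeks 2-24 are not included**

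By the week 36 sample, both arms have had open-label doses at weeks 24, 28 and 32. Values from then on should say little about the original arm.

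**The case against.** A reader might infer that the week 36 rule unblinds sites. The documents do not establish that. Section 8.2.2 does not say whether masked earlier results are handed over at week 36 or whether reporting simply starts with that visit. On the second reading the HADS footnote is met with open-label results and little is revealed. This objection stands, so the inference risk is conditional.

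A reader might also take the end-of-study wording in 8.2.2 as a third release date. It is not one: it bans independent testing and says nothing about releasing central-laboratory results. Masking to the end of the study rests only on the sentence about the sponsor.

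The rules can also be partly reconciled. The site clause in 7.6.1 has no explicit end, so 8.2.2 could supply it. For the sponsor, 7.6.1 may be a minimum and 8.2.2 a best-efforts extension. That is possible, but neither section refers to the other, and the sponsor sentence is not limited to the operational team.

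Finally, the consequences are bounded. Section 7.6.1 plans site blinding only through week 24 and then calls the study open-label. LDL-C is measured centrally, and the week 24 efficacy window closes on the first open-label dosing day for patients who enter that period (SAP Appendix 10.2). Cardiovascular events are adjudicated blind (protocol 5.3.2). Safety and quality-of-life summaries carry no formal testing (SAP 5.8, 5.12). Measures to protect the blind are deferred to a separate document (protocol 10.4.9.1), which may or may not cover site lipid release. All of this limits the harm but does not settle which release rule applies.

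**Conclusion.** The inconsistency is real and should be corrected. Sites have two incompatible release rules, patients have a HADS requirement that fails under one of them, and the sponsor has two different end dates.

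The 12-week gap is firm arithmetic. The share of patients affected is not, because accrual length and lag to lock are unstated. It is 0% if the two together are 12 weeks or less, and more than half under the assumed 26-week accrual with no lag.

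Partial inference of the double-blind arm is a possibility, not a finding. It needs weeks 2-24 values to be released at week 36, and its strength (81% to 93% against a 67% benchmark) rests on assumed correlations. Even then, what is exposed is the assessment of double-blind adverse events, data cleaning and deviation review before lock. A reader might conclude that the primary endpoint is compromised; it is not, because each affected patient's week 24 sample was drawn 12 weeks earlier. No power, sample-size or alpha figure changes.

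**What to change.** State one rule, in the same words, in sections 7.6.1 and 8.2.2 of both protocol versions:

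- Results from weeks 2-24, including the pre-dose week 24 sample, stay masked to sites, patients and the sponsor's operational team until the first-step database lock.
- From a patient's week 36 visit, only results from samples drawn after the first open-label dose may be released to sites and patients. Both arms are then on evinacumab, and the HADS footnote can be met at weeks 40 and 48.
- The request to keep the sponsor masked for the whole study applies to the operational team only, as a best-efforts extension beyond the lock. It does not cover those who run the first-step analysis.

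The ban on independent testing can stay as written, since it does not govern central-laboratory release.

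The cost is wording in two sections and a visit-based filter on the central laboratory's reports. The downside is that patients enrolled early wait longer for their double-blind values.
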